8 ADVERSE EVENTS

8.1 Definitions

An **Adverse Event** (AE) is any untoward medical occurrence, unintended disease or injury or untoward clinical signs (including abnormal laboratory findings) in subjects, users or other persons, whether or not related to the study device or procedures involved and whether anticipated or unanticipated. For users or other persons, this definition is restricted to events related to the study device.

A **Serious Adverse Event** (SAE) is any adverse event that:

- Led to death;
- Led to serious deterioration in the health of the subject that either resulted in:
 - a life-threatening illness or injury;
 - a permanent impairment of a body structure or a body function including chronic diseases;
 - in-patient or prolonged hospitalization;
 - medical or surgical intervention to prevent life-threatening illness or injury or permanent impairment to body structure or a body function;
- Led to foetal distress, foetal death, a congenital abnormality or birth defect including physical or mental impairment;

NOTE 1: Planned hospitalization for pre-existing condition, or a procedure required by the Clinical Investigation Plan, without a serious deterioration in health, is not considered a serious adverse event.

NOTE 2: Permanent impairment of a body structure or a body function - An AE, which results in a substantial disruption of a person's ability to conduct normal life functions. This does not pertain to minor events, but to serious events which result in a significant, persistent or permanent change, impairment, damage or disruption in the subject's body function/structure, physical activities and/or quality of life.

NOTE 3: Life-threatening – an event in which the subject was at risk of death at the time of the event; it does not refer to an event which hypothetically might have caused death if it were more severe.

Adverse Device Effects (ADE) and **Serious Adverse Device Effects** (SADE) are AEs related to the use of a medical device.

NOTE 1: This includes any AE resulting from insufficiencies or inadequacies in the IFU, the deployment, the implantation, the installation, the operation, or any malfunction of the medical device.

NOTE 2: This includes any event that is a result of a use error or intentional abnormal use of the medical device.

Anticipated AE means an effect, which by its nature, incidence, severity or outcome has been previously identified in the risk analysis report. The potential AEs associated with the procedures involved and study devices are listed in the current IFU.

Unanticipated Serious Adverse Device Effect (USADE) is defined as any SADE, which by its nature, incidence, severity or outcome has not been identified in the current version of the risk analysis report or IFU.

Device Deficiency is defined as an inadequacy of a medical device related to its identity, quality, durability, reliability, safety or performance. This may include malfunctions, use error or inadequacy in the information supplied by the manufacturer, including labelling.

A malfunction or deterioration is defined as the failure of a device to perform in accordance with its intended purpose when used in accordance with the manufacturer's instructions. The intended performance of a device refers to the intended use for which the device is labelled or marketed.

Reporting conventions for device deficiencies that could result in an SAE are the same as those for an actual SAE.

8.2 Investigator Assessment of AEs

For each AE, the Investigator will determine whether the event is related to the device and/or the implant procedure, whether it was anticipated or not anticipated (based on the list of potential risks provided in the IFU) and whether the event meets the definition of an SAE or USADE.

The causal relationship of the event to the device and the implant procedure will be categorized as follows:

1. **Not related:** relationship to the device or procedures can be excluded when there is no temporal relationship, the event is not a known adverse effect of similar devices or procedures, it is not clinically plausible, or the event can be attributed to another cause.
2. **Possible:** the relationship with the use of the device is weak but cannot be ruled out completely. Alternative causes are also possible (e.g. an underlying or concurrent illness/ clinical condition or/and an effect of another device, drug or treatment). Cases where relatedness cannot be assessed, or no information has been obtained should also be classified as possible.
3. **Probable:** the relationship with the use of the device seems relevant and/or the event cannot reasonably be explained by another cause, but additional information may be obtained.
4. **Causal relationship:** the event is associated with the device or with procedures beyond reasonable doubt when there is a temporal relationship, the event is a known adverse effect of similar devices or procedures, it is clinically plausible, or the event cannot be attributed to another cause.

8.3 AE Reporting Requirements

All AEs will be captured from the time of enrolment until subject participation has ended (i.e. completion of study or discontinuation). See **Section 8.3.1** for events that are not required to be reported to Edwards.

Pre-existing medical conditions or symptoms reported prior to subject enrolment will not be recorded as an AE. In the event there is a worsening in the pre-existing medical condition or symptoms due to the device or study-related procedure, then an AE must be recorded.

Death should not be recorded as an AE but should be reflected as an outcome to another specific AE.

If known, the diagnosis for an AE should be recorded, rather than listing individual signs and symptoms.

All AEs will be reported in subject medical records and the appropriate electronic case report form (eCRF) throughout the duration of the study, and will be followed until resolution, stabilization or study completion.

All SAEs and Device Deficiencies that might have led to a SAE must be reported to Edwards **immediately, but not later than 3 calendar days after site study personnel's awareness of the event.** Other AEs must be reported to Edwards as soon as practical but no later than 10 working days of awareness.

AE information must be entered into the EDC. When EDC system is not available/accessible, AE information must be reported directly via email to [contact], copying the Safety Officer of the study.

At the time of initial AE notification, the following minimal information must be provided:

- Subject ID
- AE term/diagnosis
- AE onset date
- AE seriousness
- AE device and procedure relationships

Source documentation may be requested by the Edwards Safety Officer for AEs and SAEs on a case-by-case basis (i.e., device deficiencies, device- and procedure-related events, USADEs, etc.).

The AEs will be reviewed by the Edwards Safety Officer. Each AE will be assessed as to its relationship to the study device and/or implant procedure, whether it was anticipated or not anticipated, and whether it qualifies as an SAE or USADE.

Depending on the local requirements or following agreement between both parties, Edwards or the Principal Investigator will be responsible for performing safety reporting to the EC according to the relevant local regulatory requirements.

Edwards will be responsible for reporting to the National Competent Authority according to national requirements and in line with MEDDEV 2.7/3 (Serious Adverse Event Reporting) and/or MEDDEV 2.12-1 (Medical Devices Vigilance System), as applicable.

8.3.1 Events that do not require reporting to Edwards

For purposes of this study, the following events will not be required to be reported as AEs to Edwards, because they are normally expected to occur in conjunction with transcatheter valve implantation or are associated with customary, standard care of subjects undergoing THV implantation:

- Post-operative pain.
- Post-anaesthesia emesis, nausea or headache (within 24 hours of procedure).
- Electrolyte imbalance without clinical sequelae following procedure, even if requiring correction.
- Low grade temperature increase ($\leq 101^{\circ}\text{F}$ or 38.5°C).
- Elevated white blood count, outside the standard laboratory normal value, without signs and symptoms of infection.
- Minor, localized tenderness, swelling, induration, oozing, etc. at incision / delivery system insertion site.
- Systolic or diastolic blood pressure changes that do not require treatment or intervention.
- Thrombocytopenia: does not become an AE until treatment is administered; Suspected heparin-induced thrombocytopenia should be reported.
- Hyperglycaemia – The use of insulin in the post-operative period does not constitute hyperglycaemia if during the index hospitalization. An elevated blood sugar of less than 250 mg/dL during the first 48 hours post-operative does not constitute hyperglycaemia.
- Expected, non-clinically significant events such as non-significant lab variances.
- Dizziness: imprecise term commonly used to describe various symptoms such as faintness, giddiness, imbalance, light-headedness, unsteadiness or vertigo without signs of TIA or stroke.

In addition, pre-planned future surgical procedures not associated with the study procedure or device and not due to worsening of an existing condition, do not need to be reported.

9 RISK AND BENEFIT ANALYSIS

Subjects participating in this observational study will undergo TAVI with the SAPIEN 3 Ultra THV System as part of their standard-of-care treatment for severe AS. No study-specific procedures will be performed. There are no increased risks related to the participation in this study. There are potential risks related to the overall procedure (standard cardiac catheterization, valvuloplasty and use of anaesthesia) as well as potential risks associated with the TAVI procedure, the bioprosthesis, and the use of its associated devices and accessories; risks are summarized in the IFU.

10 STATISTICAL CONSIDERATIONS

10.1 Analysis Populations

As Treated (AT) Population: Will consist of all subjects that were enrolled in the trial.

Valve Implant (VI) Population: Will consist of all enrolled subjects who receive and retain the study valve upon leaving the procedure room.

10.2 Statistical Analyses

No statistical inference will be performed, and only descriptive statistics will be presented. Descriptive statistics include number of subjects and frequencies in percentage for categorical variables and mean and standard deviation/standard error for continuous variables. Kaplan-Meier estimates will be used for time-to-event measures and where appropriate for adverse event outcomes.

11 STUDY ADMINISTRATION

11.1 General Study Organization

Edwards is the Sponsor and has the overall responsibility for the conduct of the study, including assurance that the study meets applicable regulatory requirements.

Edwards will be responsible for obtaining appropriate approvals prior to study commencement, selecting investigators, and conducting clinical site monitoring to ensure that subjects are being properly consented and the study is being conducted according to the plan. Edwards will notify investigative sites of enrolment closure.

11.2 Steering Committee

A Steering Committee will be selected to provide oversight and medical expertise to the study. Steering Committee activities are defined in the Steering Committee Charter.

11.3 Echocardiographic Core Lab

An independent echocardiographic core lab will review and analyse echocardiographic images. A manual of procedures describing current guidelines and recommendations will be provided to

the study sites prior to study initiation.

11.4 Image Management

An image transfer vendor will receive, maintain and provide angiographic and echocardiographic images to the appropriate personnel for analysis.

Instructions for image upload will be provided to study site personnel prior to study initiation. Study site personnel should make every reasonable effort to upload all images to the image transfer vendor within 5 business days of image acquisition. Any unscheduled imaging performed related to the safety or performance of the device should also be uploaded.

11.5 Histopathology

Histopathology will be performed on all explanted valves. Explants will be prepared, preserved and shipped to the Histopathology Core Lab per instructions provided by Edwards.

11.6 Study Site Personnel Training

Training by Edwards or its designee is required for study site personnel in accordance with the roles outlined in the DoA log. Training may include review of the clinical investigation plan, identification of eligible subjects, and instructions on data collection and entry.

Ongoing training may be provided by Edwards or by already trained site staff. Retraining may be performed for sites who have demonstrated protocol or implant procedure compliance issues.

Documentation of study site personnel qualifications and training will be maintained in the site's study files with copies sent to Edwards.

11.7 Data Management

This study will use a secure, password protected electronic data capture (EDC) system accessible via the Internet. A unique Subject ID will be assigned for each subject enrolled in the study. All pertinent data will be entered by the study site and core lab personnel into the eCRFs.

Every reasonable effort should be made to complete data entry within 5 business days of data collection. Data review by Edwards personnel will occur remotely as well as during on-site monitoring. Data discrepancies will be queried and resolved through the EDC system.

The site Principal Investigator or designee must ensure the accuracy and completeness of the recorded data and provide his/her electronic signature on the appropriate eCRFs at regular intervals during the study, as requested by Edwards. If changes are made to data previously signed-off, a new electronic signature will be required to acknowledge/approve the changes.

11.8 Monitoring Procedures

All study sites will be monitored periodically by Edwards or designee to ensure compliance with

the plan and the Investigator's Agreement, and that all study subjects have been properly consented. The monitor will ensure that the completed eCRFs match the medical records and work with the site to resolve differences through queries or formal action items.

11.9 Site Discontinuation

Edwards has the right to discontinue an Investigator or study site for the following reasons:

- Failure of the Investigator to enrol subjects into the study at an acceptable rate
- Failure of the Investigator to comply with pertinent regulations of appropriate regulatory authorities
- Insufficient adherence to plan requirements
- Submission of knowingly false information from the research facility to Edwards, Study Monitor, EC or appropriate regulatory authority.

If a study site is discontinued, subjects enrolled prior to discontinuation will continue to be followed per the plan.

11.10 Auditing

The study site may be subject to a quality assurance audit by Edwards or a designee, as well as inspection by appropriate regulatory authorities. It is important that the Investigator and relevant study site personnel are available during any audits and that sufficient time is devoted to the process. In the event of an audit by regulatory authorities, the Investigator should contact Edwards as soon as possible.

11.11 Publication Policy

Publication or presentation of the overall clinical study results and/or site-specific results requires prior written approval of Edwards. If Edwards approves the publication or presentation of the overall clinical study results and/or site-specific results, then Institutions and Investigators will comply with the Publications and Public Disclosure Section of the Clinical Trial Agreement. Edwards will provide statistical support for the publication process.

Results from this study will be made publicly available.

12 ETHICAL AND REGULATORY CONSIDERATIONS

12.1 Applicable Principles and Regulations

The study will be performed in accordance with the ethical principles that have their origin in the Declaration of Helsinki (as updated in Fortaleza Brazil in 2013).

The following regulations and guidelines will be followed, as applicable:

- ISO 14155: 2020 Clinical Investigation of Medical Devices for Human Subjects - Good Clinical Practice
- Medical Device Regulation 2017/745 (MDR)
- MDCG 2020-10/1 guidance
- General Data Protection Regulation 2016/679
- Specific country regulations will be fulfilled, as applicable.

12.2 Ethics Committee

This plan, the proposed ICF, other written subject information and any proposed advertising material for subject recruitment must be submitted to the EC for written approval. A copy of the written EC approval of the plan and ICF must be received by Edwards before recruitment of subjects into the study.

The Investigator must submit and, where necessary, obtain approval from the EC for all subsequent plan amendments and changes to the ICF.

The Investigator is responsible for obtaining annual EC approval and renewal throughout the duration of the study. Copies of the Investigator's reports and the EC continuance of approval must be sent to Edwards.

12.3 Informed Consent

Edwards will provide a sample ICF to the Investigator to prepare for use at his/her site. The site-specific ICF, and any subsequent modifications, must agree with current regulations and guidelines and must be approved by Edwards prior to submission to the EC. The reviewing EC must approve the ICF before use at the site.

Before participating in the study, each subject must give written Informed Consent after the context of the study has been fully explained in a language that is easily understood by the subject. The subject must also be given sufficient time to read and understand the ICF per local regulations, as applicable, as well as the opportunity to ask questions and have those questions answered to his/her satisfaction.

A copy of each subject's signed and dated consent form must be maintained by each Investigator in a designated clinical study administrative file. A signed copy of the consent form must be given

to each subject. The consent process must be documented in the subject's medical record; the documentation should minimally include that consent was obtained prior to participation in the study, the date consent was obtained, and confirmation that a copy of the consent was given to the subject.

12.4 Confidentiality

The Investigator is responsible for maintaining confidentiality throughout the clinical study. All data used in the analysis and reporting of this evaluation will be without identifiable reference to the subject. Authorized personnel assigned by Edwards will have access to the confidential files and will have the right to inspect and copy all records pertinent to this study.

12.5 Investigator Records

Records to be maintained by the Investigator include, but are not limited to, the following:

- Study plan and all amendments
- Signed Clinical Trial Agreement and any amendments
- EC approval letters, including continuing reviews and all amendments/changes
- EC-approved informed consent documents
- Relevant correspondence with another study site, EC, Edwards, monitor, including required reports

The following records must be maintained for each subject enrolled in the study:

- Signed ICF
- All relevant source documentation
- Supporting documentation of any AEs

All clinical sites will maintain the study records according to their country-specific record retention requirements.

12.6 Plan Amendments

The plan can be altered only by written amendments made by Edwards. The amended plan will be submitted to the EC before being distributed to sites. Each site must obtain EC approval and complete required training (if any, and as required by Delegation of Authority role) before implementing the amended plan.

12.7 Plan Deviations

Each deviation from the plan must be documented with the date and reason for the deviation and reported to Edwards as soon as possible, and to the EC per local guidelines and government regulations.

APPENDIX A ABBREVIATIONS

Abbreviation	Full Term
ADE	Adverse Device Effect
AE	Adverse Event
AT	As Treated
CTA	Computed Tomography Angiography
EC	Ethics Committee
eCRF	Electronic Case Report Form
EDC	Electronic Data Capture
ICF	Informed Consent Form
IFU	Instructions for Use
NYHA	New York Heart Association
SADE	Serious Adverse Device Effect
SAE	Serious Adverse Event
STS	Society of Thoracic Surgeons
TAVI	Transcatheter Aortic Valve Implantation
THV	Transcatheter Heart Valve
TEE	Transoesophageal Echocardiogram
TTE	Transthoracic Echocardiogram
USADE	Unanticipated Serious Adverse Device Effect
VI	Valve Implant

APPENDIX B DEFINITIONS

Term	Definition	Reference/ Justification
Arrhythmia / Conduction System Injury (Defect)	
Arrhythmia: an irregular heart rate (increased > 100 beats/min or decreased < 60 beats/min) or abnormal rhythm resulting in symptoms or requiring medical intervention.
 
Conduction system defect: an impairment of the electrical pathways and specialized muscular fibres that conduct impulses through the heart (ex. bundle branch block, heart block, internodal fibres, Bundle of His, Purkinje fibres, etc.).
	Sponsor
Mortality, All-Cause	
Cardiovascular mortality Any of the following criteria:
 
 • Death due to proximate cardiac cause (e.g. myocardial infarction, cardiac tamponade, worsening heart failure) • Death caused by non-coronary vascular conditions such as neurological events, pulmonary embolism, ruptured aortic aneurysm, dissecting aneurysm, or other vascular disease • All procedure-related deaths, including those related to a complication of the procedure or treatment for a complication of the procedure • All valve-related deaths including structural or nonstructural valve dysfunction or other valve-related adverse events • Sudden or unwitnessed death • Death of unknown cause 
Non-cardiovascular mortality Any death in which the primary cause of death is clearly related to another condition (e.g. trauma, cancer, suicide).
	VARC-2
Paravalvular Leak	
Paravalvular or paraprosthetic leak (PVL) is a complication associated with the implantation of a prosthetic heart valve whether traditional (surgical) or a transcatheter (TAVR) approach.
 
PVL refers to blood flowing through a channel between the structure of the implanted valve and cardiac tissue as a result of a lack of appropriate sealing
	ESC

Term	Definition				Reference/ Justification	
Prosthetic Aortic Valve Regurgitation Criteria		Normal	Mild	Moderate/ severe	VARC-2	
	Semi-quantitative Parameters					
	Diastolic flow reversal in the descending aorta - PW	Absent or brief early diastolic	Intermediate	Prominent, holodiastolic		
	Circumferential extent of prosthetic valve paravalvular regurgitation (%) ^a	<10% 10-29% ≥30%				
	Quantitative parameters^b					
	Regurgitant volume (mL/beat)	<30 mL	30-59 mL	≥60 mL		
	Regurgitant fraction (%)	<30%	30-49%	≥50%		
	EROA (cm ²)	0.10 cm ²	0.10-0.29 cm ²	≥0.30 cm ²		
	^a Not well-validated and may overestimate the severity compared with the quantitative Doppler. Circumferential extent of PVR best not to be used alone, but in combination with vena contracta width and/or area.					
	^b For LVOT >2.5 cm, significant stenosis criteria is <0.20.					
Prosthetic Aortic Valve Stenosis Criteria ^a		Normal	Mild	Moderate/ severe	VARC-2	
	Quantitative Parameters (flow-dependent)^b					
	Peak velocity (m/s)	<3 m/s	3-4 m/s	>4 m/s		
	Mean gradient (mmHg)	<20 mmHg	20-40 mmHg	>40 mmHg		
	Quantitative parameters (flow-independent)					
	Doppler velocity index ^c	>0.35	0.35-0.25	<0.25		
	Effective orifice area ^d	>1.1 cm ²	>1.1-0.8 cm ²	<0.8 cm ²		
	Effective orifice area ^e	>0.9 cm ²	>0.9-0.6 cm ²	<0.6 cm ²		
^a In conditions of normal or near normal stroke volume (50–70 mL).	^b These parameters are more affected by flow, including concomitant aortic regurgitation.					
^c For LVOT >2.5 cm, significant stenosis criteria is <0.20.	^d Use in setting of BSA ≥1.6 cm ² (note: dependent on the size of the valve and the size of the native annulus).					
^e Use in setting of BSA <1.6 cm ² .						
Reintervention	Any intervention that repairs, alters or replaces a previously implanted or operated valve, which occurs after the completion of the valve implant procedure and the transfer to the procedure room. These interventions include: 
 • Balloon aortic valvuloplasty • Surgical aortic valve replacement • Valve in valve • Paravalvular leak closure 				STS/AATS	

Term	Definition	Reference/ Justification
Stroke / Transient Ischemic Attack (TIA)	
Diagnostic Criteria
 
Acute episode of a focal or global neurological deficit with at least one of the following:
 
 • change in level of consciousness • hemiplegia • hemiparesis • numbness or sensory loss affecting one side of the body • dysphasia or aphasia • hemianopia • amaurosis fugax • or other neurological signs or symptoms consistent with stroke 
Duration of a focal or global neurological deficit >24 h; OR <24 h, if available neuroimaging documents a new haemorrhage or infarct; OR the neurological deficit results in death
 
No other readily identifiable nonstroke cause for the clinical presentation (e.g., brain tumour, trauma, infection, hypoglycaemia, peripheral lesion, pharmacological influences) to be determined by or in conjunction with designated neurologist*
 
Confirmation of the diagnosis by at least one of the following[#]:
 
 • Neurology or neurosurgical specialist • Neuroimaging procedure (MR or CT scan) • Clinical presentation alone 
Stroke definitions[†]:
 
 • Non-disabling: a mRS score of less than 2 at 90 days or the last available clinical visit with evaluable data or one that does not result in an increase of at least one mRS category from an individual's pre-stroke baseline • Disabling: a mRS score of 2 or more at 90 days or the last available clinical visit with evaluable data and an increase of at least one mRS category from an individual's pre-stroke baseline 
Stroke classification:
 
 • Haemorrhagic: an acute episode of focal or global cerebral or spinal dysfunction caused by intraparenchymal, intraventricular, or subarachnoid haemorrhage. • Ischemic: an acute symptomatic episode of focal cerebral, spinal, or retinal dysfunction caused by an infarction of the central nervous system tissue • Undetermined: stroke with insufficient information to allow categorization as ischemic or haemorrhagic. 
Transient Ischemic Attack (TIA)
 
Duration of focal or global neurological deficit <24 h, any variable neuroimaging does not demonstrate a new haemorrhage or infarct
 
*Subjects with non-focal global encephalopathy will not be reported as a stroke without unequivocal evidence based upon neuroimaging studies.
 
#If a stroke is reported without evidence of confirmation of the diagnosis by one of these methods, the event may still be considered a stroke based on the clinical presentation alone.
 
†Modified Rankin score assessments should be made by qualified individuals according to a certification process.
	VARC-2

Term	Definition	Reference/ Justification
Vulnerable Population	Individuals who are unable to fully understand all aspects of the investigation that are relevant to the decision to participate, or who could be manipulated or unduly influenced as a result of a compromised position, expectation of benefits or fear of retaliatory response	ISO 14155:2020

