5 OUTCOME MEASURES

The outcome measures for the study are as follows:

- Death
- Stroke
- New requirement for permanent pacemaker
- Aortic valve reintervention
- Valve haemodynamics
 - Aortic regurgitation
 - Mean aortic valve gradient
 - Effective orifice area
- Length of index hospitalization
- Discharge location

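### Do the stray stenosis footnote and the shared column headings in Appendix B's regurgitation table misgrade aortic regurgitation?

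*Combined protocol and SAP*

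**What the plan says.** Section 5 lists "Aortic regurgitation" among the valve haemodynamic outcomes. Section 10.2 reports "number of subjects and frequencies in percentage for categorical variables" and rules out inference.

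Appendix B has two adjacent tables, both referenced to VARC-2: one titled "Prosthetic Aortic Valve Regurgitation Criteria" and its counterpart for prosthetic stenosis. Each has three columns: Normal, Mild and Moderate/severe. The regurgitation table has five rows: diastolic flow reversal, circumferential extent, regurgitant volume, regurgitant fraction and EROA. Its first column for flow reversal reads "Absent or brief early diastolic".

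The last three rows come under a subheading marked b, and footnote b reads "For LVOT >2.5 cm, significant stenosis criteria is <0.20". The stenosis table prints the same sentence as its footnote c, attached to the Doppler velocity index. Footnote a of the regurgitation table, on circumferential extent, begins "Not well-validated and may overestimate the severity compared with the quantitative Doppler".

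Section 11.3 has an independent core lab analyse the echocardiograms. It adds that "A manual of procedures describing current guidelines and recommendations will be provided to" the study sites. Section 7.2 names VARC-2 and echocardiographic recommendations as expected standards, and Section 7.3 refers to an imaging reference guide.

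**The concern.** Text from one table has plainly ended up in the other. Once one carry-over is certain, it is natural to ask whether the column headings came with it, since all three match the stenosis table's. The printed bands invite the question: on the "Regurgitant fraction" row, any value below 30% is labelled Normal, and Moderate/severe begins only at 50%.

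If the headings belonged one grade higher, counts taken from the volume and fraction rows would understate regurgitation, always in the device's favour. In a purely descriptive study the percentages are the result. Appendix B is also the only grading scale printed in the plan, so no second table in it would expose the error.

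**Working it through.** No sample size, power or error rate is involved. The check is a lookup and a comparison of the two tables.

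**1. Reproduce the printed reading.** Inputs are the Appendix B cut-points.

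| Row | Normal | Mild | Moderate/severe |
|---|---|---|---|
| Regurgitant volume (mL/beat) | <30 | 30–59 | ≥60 |
| Regurgitant fraction (%) | <30 | 30–49 | ≥50 |

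A fraction of 29% gives 29 < 30, hence Normal. A volume of 29 mL also gives 29 < 30, hence Normal. The reading is correct for those rows. The EROA and circumferential rows are not used for cut-points because their cells may have been damaged when the PDF was read.

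**2. Can footnote b change a grade?** Compare its content with the rows that carry marker b.

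- Units: the note gives 0.20 with no unit. The rows are in mL/beat, % and cm².
- Direction: the note flags low values (<0.20). All three marked rows worsen as values rise.
- Subject: the note concerns stenosis. The regurgitation table has no stenosis criterion and no Doppler velocity index row.
- Proper home: in the stenosis table the Doppler velocity index runs >0.35, 0.35–0.25, <0.25. It worsens downward and has no unit, so a limit of <0.20 fits there.

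None of the 3 marked rows can take the note. PDF reading does not explain it either, because the sentence appears twice under different letters, each matched to a marker in its own table. The note is misplaced, but no grade can be reached through it.

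**3. Do the documents show that the headings are wrong?**

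- Three of three headings agree between the tables. That fits copying, and it fits equally well with two tables that share a layout because they come from one source.
- The documents print no alternative headings and do not reproduce the cited source.
- The flow-reversal row places absent or brief early reversal under Normal, where absent reads naturally. That favours the headings as printed.
- The direction of any error, one grade too low, is an assumption. It is also loosely defined, since the third column merges moderate with severe.

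**4. Size if the assumption held.** The moderate-or-worse threshold would move by 60 − 30 = 30 mL and by 50 − 30 = 20 percentage points. Values of 30–59 mL or 30–49% would leave Mild, and values below 30 would leave Normal. This concerns two of five rows. The documents give no distribution of regurgitation, so no number of subjects follows.

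**5. Would a row label become the reported grade?** One row is not the overall grade, and the plan prints no rule for rows that disagree. Footnote a does not settle it by ranking the quantitative rows first. It warns about circumferential extent and then advises combining that measure with vena contracta width or area, neither of which is a row in the table. The plan nowhere says that grades are read mechanically from single Appendix B rows.

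**The case for a change.** The best case for acting is that this is the only printed scale for a listed outcome, that it contains a proven copying error, and that checking one table against its source costs almost nothing. The plan also does not name the scale the core lab will use: the manual in Section 11.3 goes to the sites, and Sections 7.2 and 7.3 point to guidance without stating grades. The moderate boundary is one readers will look for, since the FAST-TAVI discharge criteria in Table 1 refer to it.

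Much of this stands. Footnote b is wrong, and whatever note was meant to be there is missing. A proofread of the table against its cited source, headings included, is ordinary housekeeping. The core lab's scale is a detail left unstated.

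The step from a stray footnote to mislabelled columns does not stand. It needs the content of a source that the documents do not reproduce, and the one qualitative row that bears on it leans the other way. Asking that the study report on Appendix B's own classes is a separate preference about reporting and does not follow from a misplaced note. The missing detail is one that an independent core lab working to VARC-2 and the cited echocardiographic recommendations can be expected to supply.

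**Conclusion.** No change to the plan follows. The proven part is a clerical slip with no effect on results: one footnote in the wrong table, applicable to 0 of the 3 rows that carry its marker. Removing it would alter no grade, count or percentage.

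The part that would matter is unproven. The shift of 30 mL and 20 percentage points arises only if the headings are one grade too low, and the documents neither show this nor offer another scale. No understatement of regurgitation should be claimed from them.

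Two conditions support this reading: no hypothesis is tested and no regurgitation threshold drives a study decision, and the echocardiograms are read by an independent core lab rather than graded from a single row. If the cited source were found to print different headings, the conclusion on the headings would have to be revisited. The conclusion on the footnote would not.
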